#### 3.5.2. Laboratory Data

Safety laboratory tests will be performed as described in the protocol.

To determine if there are any clinically significant laboratory abnormalities, the haematological, clinical chemistry (serum) and urinalysis safety tests will be assessed against the criteria specified in the sponsor reporting standards. The assessment will not take into account whether each participants's baseline test result is within or outside the laboratory reference range for the particular laboratory parameter.

For Periods 1 to 3, the baseline measurement is the predose measurement on Day -1 in each period. Changes from baseline will be defined as the change between the postdose and baseline measurements in each period.

## 3.5.3. Vital Signs

Supine blood pressure (BP) and pulse rate (PR) will be measured at times specified in the SoA given in the protocol.

For Periods 1 to 3, the baseline measurement is the predose measurement on Day 1 in each period. Changes from baseline will be defined as the change between the postdose and baseline measurements in each period.

- The maximum decrease from baseline over all measurements taken post-dose for supine blood pressure.
- The maximum increase from baseline over all measurements taken post-dose for supine pulse rate.

The maximum increase from baseline will be calculated by first subtracting the baseline value from each post-dose measurement to give the change from baseline. The maximum of these values over the respective period will then be selected, except in the case where a participant does not show an increase. In such an instance, the minimum decrease should be taken.

Similarly, the maximum decrease from baseline will be determined by selecting the minimum value of the changes from baseline. In cases where a participant does not show a decrease, the minimum increase should be taken.

If 3 of more participants have an unplanned measurements at the same timepoint these may be summarized in addition to the planned timepoints.

## 3.5.4. Electrocardiograms

A 12-lead ECG will be obtained on all participants at screening. 12-lead ECGs will be recorded on all participants at times detailed in the SoA given in the protocol. Triplicate measurements will be performed.

The QT, QTcF, PR, QRS and heart rate (HR) will be recorded at each assessment time. The average of the triplicate readings collected (where applicable) at each assessment time will be calculated for each ECG parameter. If not supplied, QTcF will be derived using Fridericia's heart rate correction formula:

QTcF = QT / (RR)
$$^(1/3)$$
 where RR = 60/HR (if not provided)

For Periods 1 to 3, the baseline value is the average of the triplicate ECG measurements collected before dose administration on Day 1 in each period. Changes from baseline will be defined as the change between the average of the postdose triplicate ECG measurements and the baseline ECG.

The following ECG endpoints will be determined:

- Change from baseline in QT interval, heart rate, QTcF interval, PR interval, and QRS complex.
- The maximum absolute value (post-dose) will be calculated for QTcF, PR and QRS.
- The maximum increase from baseline over all measurements taken post-dose will be calculated for QTcF.

The maximum increase from baseline will be calculated by first subtracting the baseline value from each postdose measurement to give the change from baseline. The maximum of these values over the respective period will then be selected, except in the case where a participant does not show an increase. In such an instance, the minimum decrease should be taken.

#### 4. ANALYSIS SETS (POPULATIONS FOR ANALYSIS)

Data for all participants will be assessed to determine if participants meet the criteria for inclusion in each analysis population prior to unblinding and releasing the database and classifications will be documented per standard operating procedures.

Participant Analysis Set	Description
Enrolled	"Enrolled" means a participant, or their legally authorized representative's, agreement to participate in a clinical study following completion of the informed consent process and randomization to study intervention. A participant will be considered enrolled if the informed consent is not withdrawn prior to participating in any study activity after screening. Potential participants who are screened for the purpose of determining eligibility for the study, but do not participate in

Participant Analysis Set	Description
	the study, are not considered enrolled, unless otherwise specified by the protocol.
Safety Analysis Set	All participants randomly assigned to study intervention and who take at least 1 dose of study intervention. Participants will be analyzed according to the product they actually received.
PK Concentration	All participants randomly assigned to study intervention and
Population	who take at least 1 dose of study intervention and in whom at
	least 1 concentration value can be reported.
PK Parameter Analysis	All participants randomly assigned to study intervention and
Population	who take at least 1 dose of study intervention and in whom at
	least 1 of the PK parameters of interest can be reported.

#### 5. GENERAL METHODOLOGY AND CONVENTIONS

Final analysis will be performed after study participant data set release following the last participant last visit.

# 5.1. Hypotheses and Decision Rules

No statistical hypothesis will be tested in this study.

#### 5.2. General Methods

Descriptive analyses will be performed. Some measures will be summarized using graphical representations.

Summaries by treatment will include summaries by administrated dose and fed/fasted condition, when applicable.

#### 5.2.1. Analyses for Binary/Categorical Endpoints

For binary or categorical variables, number of participants, numbers and percentages of participants meeting the categorical criteria will be presented in accordance with the sponsor reporting standards.

#### **5.2.2.** Analyses for Continuous Endpoints

For continuous variables, the data will be summarized using the number of participants, mean, median, standard deviation (SD), minimum, and maximum in accordance with the sponsor reporting standards. For appropriate PK parameters, geometric mean and geometric coefficient of variation (%CV) will also be summarized.

Log transformed continuous variables will be presented using summary statistics: number of observations, arithmetic mean, median, cv%, standard deviation, minimum, maximum, geometric mean and geometric cv%.

#### 5.3. Methods to Manage Missing Data

#### 5.3.1. Pharmacokinetic Data

Methods to handle missing PK data are described below.

## **Concentrations Below the Limit of Quantification:**

In all data presentations (except listings), concentrations below the limit of quantification (BLQ) will be set to zero. In listings BLQ values will be reported as "<LLQ", where LLQ will be replaced with the value for the lower limit of quantification.

## **Deviations, Missing Concentrations and Anomalous Values:**

In summary tables and plots of mean/median profiles, statistics will be calculated having set concentrations to missing if one of the following cases is true:

- 1. A concentration has been collected as ND (ie, not done) or NS (ie, no sample).
- 2. A deviation in sampling time is of sufficient concern or a concentration has been flagged as anomalous by the pharmacokineticist.

Note that summary statistics will not be presented at a particular time point if more than 50% of the data are missing.

An anomalous concentration value is one that, after verification of bioanalytical validity, is grossly inconsistent with other concentration data from the same individual or from other participants. For example, a BLQ concentration that is between quantifiable values from the same dose is considered as anomalous. Anomalous concentration values may be excluded from PK analysis at the discretion of the PK analyst or pharmacokineticist.

#### PK Parameters:

Actual PK sampling times will be used in the derivation of PK parameters. If a PK parameter cannot be derived from a participant's concentration data, the parameter will be coded as NC (ie, not calculated). (Note that NC values will not be generated beyond the day that a participant discontinues). In summary tables, statistics will be calculated by setting NC values to missing; and statistics will be presented for a particular treatment with ≥3 evaluable measurements. PK parameter analyses will not be performed for a particular parameter if more than 50% of the data are NC.

If an individual participant has a known biased estimate of a PK parameter (due for example to an unexpected event such as vomiting before all the compound is adequately absorbed from the gastrointestinal tract), this will be footnoted in summary tables and will not be included in the calculation of summary statistics or statistical analyses.

#### 5.3.2. Safety Data

For the analysis of safety endpoints, the sponsor data standard rules for imputation will be applied.

#### 6. ANALYSES AND SUMMARIES

#### 6.1. Primary Endpoints

The primary endpoints are related to safety/tolerability and their analyses are described Section 6.6.

## 6.2. Secondary Endpoints

## 6.2.1. PK parameters of sisunatovir

The secondary endpoints are related to PK and are described herein.

## PK parameter summaries:

The plasma sisunatovir PK parameters detailed in Section 3.2.1 will be listed and summarized descriptively by treatment in accordance with Pfizer data standards for the PK Parameter Analysis Population, as data permit. Missing values will be handled as detailed in Section 5.3.1. Each PK parameter will be summarized by treatment and will include the set of summary statistics as specified in Table 4.

Table 4. PK Parameters to be Summarized Descriptively by Treatment and Day

Parameter	Summary Statistics
$AUC_{tau}$ , $AUC_{tau}$ (dn), $C_{max}$ ,	N, arithmetic mean, median, SD, %CV, minimum, maximum,
$C_{max}(dn)$ , $CL/F^a$ , $V_z/F^a$ ,	geometric mean and geometric %CV
R ac , R a c , C max	
$T_{max}$	N, median, minimum, maximum
t 1/2	N, arithmetic mean, median, SD, %CV, minimum, maximum

a. Applicable for Day 5 only

To assess the relationship between the PK parameters and dose, dose normalized Cmax, AUCtau of sisunatovir will be plotted against dose (using a logarithmic scale), and will include individual participant values and the geometric means for each dose. Geometric means will have a different symbol than the individual values. The values will be dose normalized (to a 1 mg dose) by dividing the individual values and raw geometric means by dose. A footnote will be added to the plots to indicate that geometric means are presented.

All dose normalized parameters will be listed along with other individual PK parameters.

Box and whisker plots for individual participant parameters (AUCtau and Cmax) will be presented by treatment and overlaid with geometric means. These plots may be presented for both the dose-normalized and non dose-normalized versions of these parameters, as data permit.

#### PK concentration summaries:

The plasma concentrations of sisunatovir will be listed and descriptively summarized by nominal PK sampling time and treatment for the PK Concentration Population. Individual participant and summary profiles (mean and median plots) of the plasma concentration-time data will be plotted by treatment using actual and nominal times, respectively. Mean and median sisunatovir plasma concentration profiles will be presented on both linear and semilog scales.

Presentations for sisunatovir plasma concentrations will include:

- A listing of all concentrations sorted by participant ID, treatment, and nominal time postdose. The concentration listing will also include the actual times. Deviations from the nominal time will be provided in a separate listing.
- A summary of concentrations by treatment and nominal time postdose, where the set of statistics will include n, mean, median, SD, %CV, minimum, maximum and the number of concentrations above the LLO.
- Median concentrations time plots (on both linear and semi-log scales) against nominal time postdose by treatment (all treatments on the same plot per scale, based on the summary of concentrations by treatment and time postdose).
- Mean concentrations time plots (on both linear and semi-log scales) against nominal time
  postdose by treatment (all treatments on the same plot per scale, based on the summary of
  concentrations by treatment and time postdose).
- Individual concentration time plots by treatment (on both linear and semi-log scales) against actual time postdose (there will be separate spaghetti plots for each treatment per scale).
- Individual concentration time plots by participant (on both linear and semi-log scales) against actual time postdose [there will be separate plots for each participant (containing all treatments) per scale].

#### 6.2.2. Food effect on the PK of sisunatovir

For the food effect evaluation, natural log transformed AUCtau, and Cmax of sisunatovir will be analyzed using a mixed effect model with sequence, and treatment as fixed effects and participant within sequence as a random effect. The Kenward-Roger adjustment for the degrees of freedom will be used. Estimates of the adjusted mean differences (Test Reference) and corresponding 90% CIs will be obtained from the model. The adjusted mean differences and 90% CIs for the differences will be exponentiated to provide estimates of the ratio of

adjusted geometric means (Test/Reference) and 90% CI for the ratios. Treatment D (sisunatovir the highest tolerated dose Q12 hours administered under fasted condition) is the Reference treatment and Treatment A (sisunatovir the highest tolerated dose Q12 hours administered under fed condition) is the Test treatment. For the food effect comparison only the data from treatment A and D will be included in the model.

For AUCtau and Cmax a listing of the individual participant ratios (Treatment A (fed)/Treatment D (fasted)) will be provided. Box and whisker plots for individual participant parameters (AUCtau and Cmax) will be presented by treatment and overlaid with geometric means.

Residuals from the model will be examined for normality and the presence of outliers via visual inspection of plots of residuals vs predicted values and normal probability plots of residuals but these will not be included in the CSR. If there are major deviations from normality or outliers then the effect of these on the conclusions will be investigated through alternative transformations and/or analyses excluding outliers. Justification for any alternative to the planned analysis will be provided in the clinical study report.

#### **6.2.3.** Palatability of sisunatovir

The sensory attributes (mouth feel, bitterness, sweetness, sourness, saltiness, tongue/mouth burn, overall liking) from the taste questionnaires (for questionnaire tool please see protocol) will be listed and descriptively summarized by treatment sequence, and question across participants. Summary statistics (mean and 90% CI) will be calculated for the various questions. Radar plots for each of 4 time points, summarizing all attributes will be generated. Boxplots of each attribute will be plotted against the time points.

Palatability of sisunatovir may be analyzed using a mixed effect model with treatment and period as fixed effects and participant as a random effect(data permitting). Estimates and corresponding 90% CIs will be obtained from the model.

CCI	
Parameter	Summary Statistics
AUC tau	N, arithmetic mean, median, cv%, standard
Tmax	deviation, minimum,
Cmax	maximum, geometric mean and geometric
	cv%.
CCI	

- a listing of all concentrations sorted by participant ID, treatment, matrix and nominal time post-dose. The concentration listing will also include the actual times. Deviations from the nominal time will be given in a separate listing.
- a summary of concentrations by treatment and nominal time post-dose, where the set of statistics will include n, mean, median, standard deviation, coefficient of variation (cv), minimum, maximum and the number of concentrations above the lower limit of quantification.
- individual concentration-time plots by treatment (on both linear and semi-log scales) against actual time post-dose (there will be separate spaghetti plots for each dose per scale).
- median concentrations-time plots (on both linear and semi-log scales) against nominal time post-dose by treatment (all treatment on the same plot per scale, based on the summary of concentrations by dose and time post-dose).
- mean concentrations-time plots (on both linear and semi-log scales) against nominal time post-dose by treatment (all treatment on the same plot per scale, based on the summary of concentrations by dose and time post-dose).

For summary statistics, median and mean plots by sampling time, the nominal PK sampling time will be used, for individual participant plots by time, the actual PK sampling time will be used.

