In Cohort 1 only, the palatability of sisunatovir will be assessed to aid in development of pediatric formulations. These assessments will be conducted at least 48 hours after the last dose in Period 3, to allow for collection of the final PK sample and complete assessment of and AEs associated with the multiple dosing scheme. Palatability will be assessed by all participants in 4 different vehicles with a minimum of 1 hour between each vehicle, 1 hour washout has been used for the palatability assessment of other compounds. In each case, the drug in vehicle will be swirled in the mouth and spat out since it is not necessary to consume the drug to assess palatability. API blend in Pharmacopeial grade water will be used to assess the taste of the API blend. API blend in formula milk and apple juice will inform whether food vehicles are likely to improve palatability. API blend in saline will enable understanding of whether saline reduces bitter perception and improves palatability.

The highest dose planned in this study (400 mg Q12 hours x 4 days plus 1 dose) is slightly higher than the previous highest multiple oral dose tested (350 mg Q12 hours x 5 days). For

this reason, in addition to AE monitoring, labs, vitals and ECGs will also be assessed. In order to facilitate possible PK/QTc modeling, appropriate ECG measures will be taken.

As this is healthy participant study, the use of concomitant medications in this study is expected to be minimal. Nevertheless, according to the DDI risk assessment for sisunatovir as described in [Section 2.2.2](#), sisunatovir is a moderate inhibitor of CYP3A4 and is projected to be a weak inhibitor of CYP2B6. For this reason sensitive and naïve to CYP3A4 substrates and sensitive naïve to CYP2B6 substrates are prohibited in this study. Since sisunatovir is a Pgp and CYP3A4 substrate, strong and moderate CYP3A4 inhibitors and strong Pgp inhibitors are also prohibited. Lastly, due to risk of MATE1 and OCT1 inhibition, sensitive substrates of these transporters are prohibited.

CCI

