## 2.2. Study Objectives, Endpoints, and Estimands

The following are the objectives and endpoints in this study. Estimand framework will not be applied to this Phase 1 study in healthy participants.

Objectives	Endpoints
Primary:	Primary:
• To characterize the safety and tolerability of multiple oral doses of sisunatovir in healthy adult participants	Assessment of TEAEs, clinical laboratory abnormalities, vital signs, and 12-lead ECGs
Secondary:	Secondary:
To characterize the PK of multiple oral doses of sisunatovir	• PK Parameters AUC tau , C max , T max , AUC tau (dn), C max (dn) for Day 1 and AUC tau , C max , T max , AUC tau (dn), C max (dn), CL/F R ac , R ac,Cmax ; and t 1/2 and V z /F (if data permits) post last dose on Day 5
• To evaluate the effect of food on the PK of multiple oral doses of sisunatovir	• The ratio of AUC tau and C max , on Day 5; T max on Day 5
To characterize the impact of liquid vehicles on the palatability of sisunatovir	Palatability Assessment Questionnaire Scoring Metrics: mouth feel, bitterness, sweetness, sourness, saltiness, tongue/mouth burn, overall liking
CCI	

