During Periods 4-7 participants will taste sisunatovir 50 mg capsule content in different dosing vehicles ((E) water, (F) infant formula, (G) apple juice, and (H) saline) in a cross over manner and then spit out the drug with the intention of assessing the palatability of sisunatovir in different dosing vehicles. The palatability questionnaire will be completed for each vehicle, the questionnaire asks participants to assess each vehicle at 4 different time increments after tasting. At least 60 minutes will pass between tasting each vehicle. Period 4 may start after the last PK draw of Period 3.

Cohort 2 is an optional randomized, crossover cohort with 3 periods. Periods 1-2 are double blind, sponsor open, placebo controlled crossover design evaluating the safety, tolerability, and PK of sisunatovir administered Q12 hours for 4 days plus 1 dose in a fed state. Period 3, is an open label period to evaluate the food effect of sisunatovir given Q12 hours x 4 days plus 1 dose in a fasted state. Doses will not exceed 400 mg Q12 hours x 4 days plus 1 dose. Note that if the mean Day 5 exposure exceeds the rat NOAEL in Cohort 1, the dose in Cohort 2 will be capped at a dose that is not anticipated to exceed the rat NOAEL. Cohort 2 will be conducted at the discretion of the Sponsor after review of Cohort 1 data (including PK for at least periods 1 and 2), and there will be 2 sequences of 6 participants for Cohort 2.

[figure not shown]

Figure 1. Study Schema

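### The required palatability summary in SAP 6.2.3 is grouped by treatment sequence and question, naming neither vehicle clearly nor time point, so it does not clearly address the vehicle objective

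*SAP*

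**What the plan says.** The third secondary objective in SAP section 2.2 is "To characterize the impact of liquid vehicles on the palatability of sisunatovir". In Part 2 each vehicle is a treatment in its own right: "E) water, (F) infant formula, (G) apple juice, and (H) saline" (SAP section 2.3). Protocol section 4.2 states that "Palatability will be assessed by all participants in 4 different vehicles". On timing, SAP section 2.3 says "the questionnaire asks participants to assess each vehicle at 4 different time increments after tasting"; protocol section 8.5.1 gives these as 1, 5, 10 and 20 minutes.

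SAP section 6.2.3 then sets out the analysis:

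- For the grouping, it has the attributes "listed and descriptively summarized by treatment sequence, and question across participants".
- For the statistics to be shown, it says: "Summary statistics (mean and 90% CI) will be calculated for the various questions". This is a separate sentence and names no grouping beyond the question.
- For the plots, it says: "Radar plots for each of 4 time points, summarizing all attributes will be generated". It also plans boxplots for the attributes over time. Neither plot is said to be split by vehicle.
- For a model, it says: "Palatability of sisunatovir may be analyzed using a mixed effect model with treatment and period as fixed effects". Participant would be the random effect, and the model depends on the data allowing it.

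Protocol section 9.3.3 promises a listing and a descriptive summary without naming a grouping variable. Protocol section 9.3.1 has a general rule that treatment arms and placebo are reported separately. SAP section 2.1 declares no changes to the protocol's analysis.

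**The concern.** The question is which vehicle tastes better, so the required table should have one entry per vehicle for each question and time point. The sentence that defines the table names the treatment sequence instead. In a crossover where everyone tastes every vehicle, sequence records only the order of tasting, and a summary by order averages out the comparison of interest.

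Elsewhere the SAP is explicit. Concentrations are summarised by treatment and nominal time (section 6.2.1), and ECG changes by treatment and time (section 6.6.4). Palatability has no such statement.

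A programmer following the sentence could produce a table with no vehicle comparison, or one broken into very small cells. The vehicle comparison would then rest on plots whose layout is not fixed, on an optional model, or on a table chosen after the scores have been seen. These data are meant to inform paediatric formulations.

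**Working it through.** The plan states no precision, effect size or SD for palatability, and protocol section 9.5 says the sample size is empirical. There is no planned figure to reproduce. The one available count agrees: 4 sequences × 3 participants = 12 (SAP section 2.3).

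**Inputs**

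- Vehicles: 4, Treatments E to H (SAP section 2.3).
- Each participant tastes all 4 (protocol section 4.2), so every sequence contains every vehicle.
- Time points: 4 (protocol section 8.5.1).
- Participants: about 12 (SAP section 2.3).
- Assumption: Part 2 uses 4 sequences of 3, as stated for Cohort 1. The schema is not shown, and protocol section 6.1.1.3 says only that the order is randomised.

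**Reading 1: by sequence and question, as written**

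The expected mean of a sequence is the average of the four vehicle means plus the average of the four period effects. Both terms are the same for every sequence, because each sequence includes every vehicle and every period. Carryover aside, the sequence means have the same expectation whatever the vehicle effects are.

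For illustration, take assumed vehicle means of 70, 40, 30 and 60 on the 0 to 100 scale. Each sequence mean is (70 + 40 + 30 + 60)/4 = 50. The vehicles differ by up to 40 points, and the table shows 50 four times.

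If the time points were also combined, one sequence-by-question cell would hold 3 participants × 4 vehicles × 4 times = 48 correlated ratings. No rule is given for a confidence interval on such a cell.

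**Reading 2: by treatment, sequence and question, fully crossed**

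Vehicles are kept apart, but each cell holds about 3 participants. The 90% CI half-width for a mean, in SD units, is t(0.95, n − 1)/√n:

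| Grouping | n | Formula | Half-width |
|---|---|---|---|
| Vehicle within sequence | 3 | t(0.95, 2)/√3 | 1.686 SD |
| Vehicle, all participants | 12 | t(0.95, 11)/√12 | 0.518 SD |

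The ratio is 1.686/0.518 = 3.25, so the interval is about 3.25 times as wide as the same data would give when grouped by vehicle.

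**Reading 3: separate tables by treatment and by sequence**

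A three-item list could also mean separate displays. The display by treatment would then have n = 12 per vehicle and a half-width of 0.518 SD. This is the useful table, but the sentence does not establish it.

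Under all three readings, the sentence leaves time point unstated.

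**The case against.** The strongest reply is that this is a drafting slip with an obvious intended meaning. Four arguments support it.

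*A comma may be missing.* The SAP text as read from the PDF has lost punctuation elsewhere, for example between two PK parameters in section 2.2, so the intended list may have been treatment, sequence and question. This stands as a possibility. The comma before the last item does not settle it, because SAP section 6.2.2 puts the same comma in a two-item list of fixed effects. Neither reading can be treated as established.

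*The vehicle objective can still be met.* A reader might infer that the plan cannot answer the vehicle question at all. The documents do not support that. The scores are listed, the questionnaire form in protocol Appendix 10 records the treatment, and the mixed model in SAP section 6.2.3 would estimate vehicle effects with 90% CIs. The weakness is that the model is optional and the required table does not clearly do the job.

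*Protocol section 9.3.1 requires separate reporting by treatment.* This points to the likely intent. It does not override a specific sentence that names a different grouping, and the SAP declares no modification that would reconcile the two.

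*Pooling over time is not stated.* A reader might infer that the 1, 5, 10 and 20 minute ratings will be combined. The SAP does not say so: the radar plots are drawn per time point and the boxplots against time. What stands is only that the summary sentence omits time point.

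**Conclusion.** The point holds as a specification fault. The only required palatability summary has a grouping that is either wrong for the objective (Reading 1), needlessly imprecise (Reading 2) or left to guesswork (Reading 3). The plots do not name the vehicle, and the one palatability analysis that names treatment is optional, so no required output clearly delivers the vehicle comparison.

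The zero vehicle contrast applies only to the literal reading and sets carryover aside. The 1.69 SD against 0.52 SD comparison applies only if treatment is fully crossed with sequence and Part 2 uses 4 sequences of 3. The second condition cannot be checked without the schema.

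This is a minor correction. The endpoint is secondary and descriptive, no hypothesis is tested, and data collection is unaffected.

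**What to change.** In SAP section 6.2.3, replace the grouping sentence with wording such as: *Scores will be listed, and summarised by vehicle (Treatments E, F, G and H), time point (1, 5, 10 and 20 minutes) and question across all participants, with mean and 90% CI.*

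Add that the radar plots and boxplots are produced by vehicle. A display by sequence may be kept as a supplement, but not as the grouping for the main summary.

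The cost is about two sentences in the SAP and the matching table and figure layouts. No new data are needed. The change should be made before the palatability scores are analysed, so that the layout is not chosen after the results are seen.
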